Data Collection Procedures: Each patient will be approached by a study investigator for acquisition of written informed consent and Health Insurance Portability and Accountability Act authorization after being evaluated by the treating emergency physician and determined to meet study eligibility criteria. When English will not be the participant's primary language, a staff interpreter or licensed telephone interpreter would be used. Baseline pain score will be determined with an 11-point numeric rating scale (0 to 10), described to the patient as "no pain" being 0 and "the worst pain imaginable" being 10. A study investigator will record the patient's body weight and baseline vital signs. The on-duty ED pharmacist will prepare a breath-actuated nebulizer with doses of 0.75 mg/kg, 1 mg/kg, and 1.5 mg/kg according to the predetermined randomization list,

which will be created in SPSS (version 24; IBM Corp, Armonk, NY) with block randomization of every 10 participants. The medication will be delivered to the treating nurse in a blinded fashion and will be administered via breath-initiated nebulization with a minimum time of 5 min and maximum time of 15 min up to three doses.

Study investigators will record pain scores, vital signs, and adverse effects at 15, 30, 60, 90, and 120 minutes. If patients reported a pain numeric rating scale score of 5 or greater and requested additional pain relief, a second (equivalent to the first dose) of SDK via BAN will be administered to the patient in a blinded fashion. In situations when nebulized SDK will fail to achieve acceptable (by patient) pain relief or patient will refuse to continue nebulized SDK treatment, morphine at 0.1 mg/kg will be administered as a rescue analgesic.

All data will be recorded on data collection sheets, including patients' sex, demographics, medical history, and vital signs and entered into SPSS (version 24.0; IBM Corp) by the research manager. Development of the randomization list, confirmation of written consent acquisition for all participants, and statistical analyses will be conducted by the research manager and statistician, who would work independent of any data collection.

Patients will be closely monitored for any change in vital signs and for adverse effects during the entire study period (up to 2 h) by study investigators. Common adverse effects that are associated with sub-dissociative dose ketamine are feeling of unreality, dizziness, nausea, vomiting, and sedation.

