Data Analysis: Data analyses will include frequency distributions, paired t-test to assess a difference in pain scores within each group, and independent-sample t-test to assess differences in pain scores between the 3 groups at the various intervals.

Mixed-model linear regression will be used to compare changes in pain numeric rating scale across time points. This will compensate for participants lost to follow-up and allow all patients' data to be analyzed on an intention-to-treat principle.

For categorical outcomes (eg, complete resolution of pain), a X^2 or Fisher's exact test will be used to compare outcomes at 30 minutes. Percentage differences and 95% confidence intervals between the treatment groups will be calculated for all time points with $P < .05$ to denote statistical significance. Based on the validation of a verbally administered rating scale of acute pain in the ED and the comparison of verbal and visual pain scales, we will use a primary outcome consisting of a minimal clinically meaningful difference of 1.3 between three groups at the 30-minute pain assessment.^{28,29}

Sample Size: Assuming an SD of 3.0, a power analysis determined that a repeated-measures ANOVA with a sample size of 34 patients per group (102 total) will provide at least 80% power to detect a difference of at least 1.3 at 30 minutes (as well as at any other interval post-baseline), with an $\alpha = .05$. To account for possible missing data the total sample size will be 120 patients

(40 per group). A pre-planned interim data analysis will occur upon reaching a total of total of 60 patients (20) patients per group.

Expected Outcomes: The primary outcome will include a comparative reduction of pain scores on numeric rating pain scale (NRS) between recipients of nebulized SDK at three different doses at 30 minutes post-analgesic administration.

ATTACHMENTS

List any attachments (contracts, participant materials, data collection tools, etc.)

Protocol for analgesic administration via Breath Actuated Nebulizer

MAIMONIDES MEDICAL CENTER DEPARTMENT OF EMERGENCY MEDICINE (ED)

Protocol for ED Analgesics Administration via Breath-Actuated Nebulizers (BAN)

Background

[figure not shown]

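### No per-patient side-effect rate over the 2-hour period is defined: the only named categorical test is at 30 minutes, and separate time-point differences cannot supply that rate

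*Combined protocol and SAP*

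**What the plan says.** The Study Objectives pair analgesic efficacy with rates of side effects. The Hypothesis expects the 1.5 mg/kg arm to have better analgesia at 30 minutes and similar side-effect rates. The 30-minute mark belongs to the analgesia part, and no window is given for side effects.

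Data Collection Procedures: "Study investigators will record pain scores, vital signs, and adverse effects at 15, 30, 60, 90, and 120 minutes". Patients are watched "for adverse effects during the entire study period (up to 2 h) by study investigators". Each nebulization is given "with a minimum time of 5 min and maximum time of 15 min up to three doses".

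The Data Analysis section does not mention side effects by name. The relevant sentence opens "For categorical outcomes (eg, complete resolution of pain" and ends by saying that a chi-square or Fisher test "will be used to compare outcomes at 30 minutes". The next sentence reads: "Percentage differences and 95% confidence intervals between the treatment groups will be calculated for all time points", with P < .05 as the significance threshold. Frequency distributions are also planned, without a stated time. No section defines a side-effect outcome per patient over the whole observation period.

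**The concern.** An objective about rates of side effects, in patients who may be dosed more than once over two hours, is most naturally answered by the proportion of patients who had the effect at all. The plan does not ask for that number. It offers a test at one assessment and a set of differences at each assessment taken separately.

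The result could therefore misdescribe how many patients were affected in each arm. Short-lived effects in many patients and persistent effects in a few can look the same at every time point. In addition, no single comparison is marked as the safety result, so the one to be emphasised could be chosen after the data are seen.

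**Working it through.** The plan states no figure for side effects, so there is none to reproduce. The check has four steps.

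**1. What is compared, and when**

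| Item | Times (min) | Source |
|---|---|---|
| Adverse effects recorded | 15, 30, 60, 90, 120 | Data Collection Procedures |
| Named categorical test | 30 | Data Analysis |
| Between-arm percentage differences with 95% CI | all time points | Data Analysis |
| Proportion ever affected, 0 to 120 | not defined | – |

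Three of the five assessments (60, 90, 120) come after 30 minutes. All three fall within the all-time-point differences if side effects are treated as categorical outcomes. That is an inference, because the section's only example is a pain outcome.

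**2. Why cross-sections do not give the rate**

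Let p₁ to p₅ be the proportions of one arm affected at the five assessments. With complete data, the proportion ever affected at an assessment, E, is bounded by

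max(p₁,…,p₅) ≤ E ≤ min(1, p₁ + … + p₅).

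Take 40 per arm (Sample Size) and one affected patient at each assessment, so each p is 1/40 = 2.5%. Then E lies between 2.5% and 5 × 2.5% = 12.5%. Both ends can occur:

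- Arm A: five different patients, each affected at one assessment. E = 5/40 = 12.5%.
- Arm B: one patient affected at all five. E = 1/40 = 2.5%.

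The between-arm difference is 0 at every assessment, while the difference in E is 12.5% − 2.5% = 10 percentage points. The example shows what the summaries hide and does not claim a significant effect. For 5/40 against 1/40 the two-sided Fisher p is 2 × [C(40,5) × 40 + C(40,6)] / C(80,6) = 2 × (26,320,320 + 3,838,380) / 300,500,200 = 0.20.

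**3. How repeat dosing relates to the 30-minute test**

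A dose takes 5 to 15 minutes. If a second dose starts at the 15-minute assessment, it ends at 15 + 5 = 20 to 15 + 15 = 30 minutes. The trial text gives no redosing interval. If the 15-minute interval in the attached ED nebulizer protocol is assumed, a third dose starts at about 30 minutes, and its effects could appear only at 60 minutes or later.

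**4. How many comparisons the time-point approach creates**

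Data Collection Procedures lists five common effects: unreality, dizziness, nausea, vomiting and sedation. If P < .05 is applied at every time point, there are 5 effects × 5 times × 3 pairs of arms = 75 comparisons, none designated as the main one.

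**The case against.** The strongest reply is that the plan does compare the arms after 30 minutes. Differences with confidence intervals and a significance threshold are a comparison, and dizziness at 15 minutes only, or after a repeat dose, would appear at its own assessment. That stands. A reader might infer from the 30-minute test that later side effects are left out of the safety comparison. The sentence on all time points rules that out.

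It can also be said that the 30-minute test may be meant only for pain outcomes, since side effects are not named there. That is possible, but the plan then assigns no named test to side effects, and the ever-affected rate is still undefined.

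A reader might further infer that the omission favours the hypothesis of similar rates because the 1.5 mg/kg arm can accumulate the most drug (3 × 1.5 = 4.5 mg/kg, against 3 × 0.75 = 2.25 mg/kg in the lowest arm). The documents do not support a direction. Repeat dosing depends on a pain score of at least 5 and a patient request, and the hypothesis expects the top arm to have less pain. One dose of 1.5 mg/kg is less than two of 1 mg/kg (2 mg/kg) or three of 0.75 mg/kg (2.25 mg/kg). No repeat-dose rates by arm are given, and no share of late-onset effects either, so the number of events missed at 30 minutes cannot be estimated.

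Finally, an any-time rate includes events after morphine rescue. That is a fair point against relying on it alone.

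**Conclusion.** The point holds as a weakness in the choice of summary measure. Later events are not excluded. Followed as written, the plan answers its side-effect objective with a test at one assessment and five cross-sections, from which the proportion ever affected cannot be recovered. In the 40-per-arm illustration the hidden difference is 10 percentage points. The size and direction in the actual trial are unknown.

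This rests on two readings: that the rates in the objective cover the whole observation period, for which no narrower window is given, and that side effects fall under the categorical-outcome sentences. If the second reading fails, the safety analysis is less specified still.

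The change is a cheap improvement. It will not by itself establish similarity, for which no margin is stated. With 40 per arm, the 95% half-width for a pairwise difference, 1.96 × √(2p(1−p)/40), is about 13 points at an assumed common rate of 10% and 22 points at 50%.

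**What to change.** State in the Data Analysis section that the main safety comparison is the proportion of patients with at least one adverse effect at any assessment through 120 minutes, by randomised arm. Report it overall and for each named effect, using the chi-square or Fisher test already planned, with pairwise risk differences and 95% confidence intervals. Designate the overall proportion as the leading result. Keep the per-time-point percentages as description.

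Report the same result counting only events before morphine rescue, as a second summary. Rescue happens after randomisation and may differ between arms, so this should not replace the main comparison. State how patients with missed assessments are counted.

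The cost is a sentence or two and one derived variable from assessments already planned. The pre-rescue summary also needs the time of rescue. The protocol does not list this among the recorded items, so the data sheet should be checked and a field added if it is absent.

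### The stated 80% power for a 1.3-point difference at 30 minutes does not follow from SD 3.0 and 34 per group; the planned t-test has about 42%

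*Combined protocol and SAP*

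**What the plan says.** The Sample Size section opens with "Assuming an SD of 3.0" and then claims: "repeated-measures ANOVA with a sample size of 34 patients per group (102 total) will provide at least 80% power to detect a difference". It sets alpha at .05 and specifies the target as "a difference of at least 1.3 at 30 minutes (as well as at any other interval post-baseline"). Enrolment is then raised to 40 per group to allow for missing data.

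The Data Analysis section calls 1.3 the "minimal clinically meaningful difference of 1.3 between three groups at the 30-minute pain assessment". For comparing the arms it plans an "independent-sample t-test to assess differences in pain scores between the 3 groups at the various intervals". It also plans a mixed-model linear regression for changes in NRS over time. Neither is named as the primary test.

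The Hypothesis and Expected Outcomes sections place the primary outcome at one time point, the reduction in pain at 30 minutes. Nowhere does the plan give a within-patient correlation, a covariance structure, the ANOVA effect being tested, the sidedness of alpha, or whether 3.0 is the SD of the raw score or of the change.

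**The concern.** A difference of 1.3 against an SD of 3.0 is a standardised difference of 0.43. Thirty-four per arm is far too few to detect an effect of that size at one time point with 80% power. The power is credited to a repeated-measures analysis, while the comparison at each interval is a t-test that uses one reading per patient and gains nothing from the others.

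This sentence is the only justification given for the sample size. If power is really below 50%, the trial is more likely than not to miss the difference it calls clinically meaningful. A null result could then be taken as evidence that the doses relieve pain equally, because the plan appears to promise a sensitivity it does not have.

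**Working it through.** **Inputs.** Difference 1.3, SD 3.0, alpha .05, 34 per group (40 enrolled), all from Sample Size. Five post-baseline readings, at 15, 30, 60, 90 and 120 minutes, from Data Collection Procedures. Two-sided testing is my assumption, as the plan does not say. The correlation ρ is not given, so a range is shown.

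**1. Planned t-test, two arms, one time point.** The noncentrality is (1.3/3.0)·√(n/2) on 2n − 2 degrees of freedom.

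| n per arm | Noncentrality | Critical t | Power |
|---|---|---|---|
| 34 | 1.787 | 1.997 | 42.1% |
| 40 | 1.938 | 1.991 | 48.2% |
| 84 | 2.808 | 1.974 | 79.7% |
| 85 | 2.825 | 1.974 | 80.2% |

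The stated 80% is not reproduced. Solving for the difference detectable with 80% power gives 2.07 at 34 per arm and 1.90 at 40. Solving instead for the SD gives 1.885 at 34 per arm. A one-sided test at 34 per arm has 54.9%.

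**2. Three-arm one-way ANOVA at 30 minutes, 34 per arm.** λ = n·Σ(μᵢ − μ̄)²/SD².
- Means 0/0.65/1.3: λ = 34 × 0.845/9 = 3.19, power 33%.
- Means 0/0/1.3: λ = 34 × 1.127/9 = 4.26, power 43%.

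**3. Repeated-measures ANOVA, group main effect.** With m readings and equal correlation ρ, λ above is multiplied by m/(1 + (m − 1)ρ).

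| Means | m | Power at ρ = 0.5 | Largest ρ giving 80% |
|---|---|---|---|
| 0/0.65/1.3 | 5 | 52% | 0.15 |
| 0/0.65/1.3 | 6 | 53% | 0.19 |
| 0/0/1.3 | 5 | 65% | 0.29 |
| 0/0/1.3 | 6 | 66% | 0.31 |

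The six-reading rows count baseline, where randomised arms should not differ, so they are generous. Either way this tests the average over time, with the full 1.3 assumed present at every reading.

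**4. Repeated-measures ANOVA, group-by-time interaction.** Taking the 30-minute effect size as the interaction effect size (f = 0.177 or 0.204, λ = 102·f²·m/(1 − ρ), m = 5 or 6) gives 82% or more for the values tried (ρ = 0, 0.3, 0.5). This test asks whether the profiles differ anywhere, not whether two arms differ by 1.3 at 30 minutes.

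**5. Baseline-adjusted 30-minute contrast, if 3.0 is the raw-score SD.** The residual SD is 3.0·√(1 − ρ²), with ρ the baseline-to-30-minute correlation.

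| ρ | Residual SD | Power, 34 per arm |
|---|---|---|
| 0.5 | 2.60 | 53% |
| 0.7 | 2.14 | 69% |
| 0.8 | 1.80 | 84% |

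Power of 80% needs residual SD 1.885, so ρ = √(1 − (1.885/3)²) = 0.78. A change score has SD 3.0·√(2(1 − ρ)) and needs ρ = 1 − (1.885/3)²/2 = 0.80.

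**6. If 3.0 is already the SD of the change.** A t-test on the changes has the 42% of step 1. With equal variances at baseline and 30 minutes, the baseline-adjusted residual SD is 3.0·√((1 + ρ)/2). For ρ ≥ 0 this is never below 3.0/√2 = 2.12, which exceeds 1.885, so 80% is out of reach.

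**7. The hypothesis as worded.** The top dose is expected to do better than both lower doses. If each is truly 1.3 worse, the chance that both unadjusted t-tests succeed (simulation, 40,000 runs) is 26% at 34 per arm and 31% at 40. The chance that at least one succeeds is 58% and about 65%.

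**The case against.** The plan credits its 80% to a repeated-measures ANOVA, so 42% belongs to a different test. Some repeated-measures effects do exceed 80%: the main effect at low correlation, and the interaction. The plan also includes a mixed model and names no primary test. If that model adjusted for baseline, power with all 40 per arm evaluable would be 60% at a correlation of 0.5 and 76% at 0.7, so saying power is under 50% depends on taking the t-test. Finally, a 1.3-point step between adjacent doses, 2.6 across the range, gives an ANOVA power of 89% at 34 per group.

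Some of this stands. The 42% is for one unadjusted pairwise t-test and should be labelled so, and the baseline-adjusted figures depend on 3.0 being the raw-score SD. The beat-both figures are secondary, because the plan sets no rule that both comparisons must succeed.

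None of it supports the sentence as written, which claims 80% for 1.3 at 30 minutes and at every other post-baseline interval. Main-effect and interaction tests do not address a single interval. The mixed model is described for change across time points, with no baseline covariate or correlation, and would still need a correlation of about 0.73 even at 40 per arm. The adjacent-dose reading does not fit a difference of at least 1.3, and it would need 27 per group, not 34. The original calculation may have used another effect or a software default. That would explain the number without making the claim true.

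**Conclusion.** The concern holds. At 30 minutes, a two-sided t-test between two arms has 42% power for 1.3 points at 34 per arm and 48% at 40, against the stated minimum of 80%. These figures rest on SD 3.0, alpha .05 unadjusted, and equal arms. None of the comparisons tried for a 1.3-point difference between arms at that single time point reaches 80% from the stated inputs. A baseline-adjusted analysis gets there only with a correlation of about 0.78 at 34 per arm, which the plan does not state, and only if 3.0 is the raw-score SD. Because the sentence carries the whole sample-size justification for the primary outcome, it must be corrected.

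**What to change.** Replace the power sentence in Sample Size with figures that follow from its inputs, for example: *With 34 evaluable patients per group (40 enrolled), SD 3.0 and two-sided alpha .05, an unadjusted two-group comparison at 30 minutes has 42% power for a difference of 1.3 and 80% power for a difference of 2.1 (1.9 if all 40 are evaluable).*

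If the power is meant to come from a baseline-adjusted model:
- name that model as the primary analysis of the 30-minute outcome;
- say whether 3.0 is the SD of the raw score or of the change;
- state the assumed correlation and show a range. For a raw-score SD at 34 per group this is 53% at 0.5, 69% at 0.7 and 84% at 0.8.

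In either case, delete the extension to other post-baseline intervals, and state that a non-significant result will not be interpreted as equal analgesia.

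The cost is protocol and SAP wording and a less favourable stated power, with no extra patients. Rewording corrects the statement but does not raise the power. If the sponsor wants 80% for 1.3 with the t-test, the size is 85 evaluable per arm, 255 in total. At the plan's own allowance for missing data that is 85 × 40/34 = 100 enrolled per arm.
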